## 3.2 Complete Case Population

The level of missing data for each outcome will be assessed. If missing outcome data is present the initial analysis will be based on the complete cases. All tests of the effect of treatment on outcomes will be conducted on a complete case (CC) population. That is, all

Date:

20/03/2019

the recruited participants will be included in the analysis, with the exception of those with missing outcome data. This will be done on a 'by analysis' basis, i.e. only those participants with missing data for variables required for a specific analysis will be removed.

## 3.3 Intention-to-treat Population/Full analysis set

The intention-to-treat (ITT) analysis population will consist of all participants randomised. Participants will be analysed in the group to which they were randomly allocated and regardless of any protocol deviations or violations. Multiple imputation methods will be used to impute missing outcome data. This will be a sensitivity analysis.

## 3.4 Per-protocol Population

The per protocol (PP) population are those who were compliant with the protocol and have complete data for the analysis concerned on 'by analysis' basis. In the control arm, the PP population will include all participants randomised to that arm with complete outcome data. In the intervention arm, the PP population will be defined as participants who have attended at least one group session of the programme and have outcome complete data. This will be a sensitivity analysis.

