### 1.2.3 Study treatment interventions

This will be a randomised control trial with an intervention group and a control group.

1) Intervention group: Participants randomised to the intervention group will receive the standard information leaflet and will be invited to attend two group-based structured education sessions. These education sessions will be delivered by trained facilitators approximately two weeks apart. The participants will receive 82 physical activity related text messages at different weekly frequencies following the second education session up until the 12 month follow-up assessment.

These structured education sessions have been developed and refined in conjunction with PPI work and through the use of existing infrastructure consisting of Diabetes. Education and Self-Management in on-going and Newly Diagnosed (DESMOND) groups and a network of trained facilitators.

2) Control group: Participants randomised to control group will not receive the intervention. Participants will be provided with general health advice in the form of a standard information leaflet and will continue with their 'usual' GP care.

Date:

20/03/2019

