### 5.2 Primary Endpoint Analysis

### 5.2.1 Primary Analysis of Primary Endpoints

The primary outcome is change in overall volume of physical activity (average acceleration, ENMO) from baseline to 12 months. For the primary outcome treatment arm will be compared using linear regression modelling with

- 1. a binary indicator for randomisation group as the explanatory variable
- terms for stratification factors (gender and ethnicity) as confounders
- 3. adjustment for the change from baseline in accelerometer wear time and baseline average daily physical activity.

The primary analysis at 12 months will be based on complete data.

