#### 5.2.2 Sensitivity Analyses

#### 5.2.2.1 Per Protocol Population

For the PP analysis, participants who have engaged with at least one group session of the programme will be included. The PP will adhere to the same steps as the primary analysis.

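### The per-protocol sensitivity analysis compares intervention attenders with all controls, so it is a non-randomised contrast. It should be labelled as such, with a complier-average causal effect reported beside it.

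*SAP*

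**What the plan says.** SAP section 3.4 defines the PP set by arm. For controls, "In the control arm, the PP population will include all participants randomised to that arm with complete outcome data". For the intervention arm, the set is "participants who have attended at least one group session of the programme and have outcome complete data". The section then gives its role: "This will be a sensitivity analysis".

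Section 5.2.2.1 restates the rule without naming an arm: "participants who have engaged with at least one group session of the programme will be included". It fixes the model by reference: "The PP will adhere to the same steps as the primary analysis". Under section 5.2.1 that means linear regression of change in average acceleration on arm, with gender, ethnicity and "adjustment for the change from baseline in accelerometer wear time and baseline average daily physical activity".

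The SAP plans no instrumental-variable or complier analysis and states no assumption about non-attenders. Section 1.2.3 says that controls do not receive the intervention, that both arms get the leaflet, and that the 82 text messages are sent "at different weekly frequencies following the second education session up until the 12 month follow-up assessment". It does not say whether someone who attended no session gets the messages.

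**The concern.** Attendance is known only after randomisation and is chosen by the participant. Non-attenders are taken out of one arm, while their counterparts in the other arm cannot be identified and stay in. If people who turn up would have changed their activity differently anyway, the two groups differ even when the programme does nothing. The model adjusts for baseline activity, gender and ethnicity, but not for motivation or health status.

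The risk lies in interpretation. The PP result will sit among the sensitivity analyses, and section 4.1 treats any two-sided p-value below 0.05 as significant with no multiplicity adjustment. A PP estimate larger than the primary one could be taken as support for the programme when selection alone may have produced it. It does not check the primary result under a different assumption. It targets a different effect and adds a selection term.

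**Working it through.** **Inputs from the SAP.** Section 1.2.6 gives a target difference of 2.1 mg, SD 5.3 mg, 80% power and a 5% level. Section 4.1 makes tests two-sided and section 1.2.2 gives 1:1 allocation. A two-sample t calculation needs 101 per arm, or 202 in total (power 80.0%), so the SAP's evaluable number reproduces; the normal approximation gives 100 per arm. Inflation: 202 / (1 − 0.30) = 288.6, that is 289, or 290 with equal arms, which also matches. The steps below use 101 per arm and SD 5.3 mg.

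**Inputs the SAP does not give (assumed, shown over a range).**
- a = proportion of the intervention arm attending at least one session, among those with outcome data.
- g = mean 12-month change in would-be attenders minus that in would-be non-attenders, with no intervention and after covariate adjustment.

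**PP estimate.** Let m1 and m0 be the mean changes without intervention in would-be attenders and non-attenders, and d the effect in attenders.
- Intervention PP mean = m1 + d
- Control mean = a·m1 + (1 − a)·m0
- Difference = d + (1 − a)(m1 − m0) = d + (1 − a)·g

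The bias for d is (1 − a)·g, with the sign of g. With a = 0.7 and g = 2 mg: 0.3 × 2 = 0.6 mg, and 0.6 / 2.1 = 29% of the target.

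**Range.** Bias in mg. In brackets is the two-sided rejection rate when d = 0, from SE = 5.3·√(1/101 + 1/(101a)) and rejection = Φ(−1.96 − bias/SE) + 1 − Φ(1.96 − bias/SE).

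| a | g = −1 | g = 0 | g = 1 | g = 2.1 | g = 3 |
|---|---|---|---|---|---|
| 0.6 | −0.40 (7.5%) | 0 (5.0%) | +0.40 (7.5%) | +0.84 (16.4%) | +1.20 (28.6%) |
| 0.7 | −0.30 (6.5%) | 0 (5.0%) | +0.30 (6.5%) | +0.63 (12.0%) | +0.90 (19.5%) |
| 0.8 | −0.20 (5.7%) | 0 (5.0%) | +0.20 (5.7%) | +0.42 (8.3%) | +0.60 (11.8%) |
| 0.9 | −0.10 (5.2%) | 0 (5.0%) | +0.10 (5.2%) | +0.21 (5.9%) | +0.30 (6.8%) |

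For g = 1 to 3 mg the bias runs from +0.10 mg (5% of 2.1) to +1.20 mg (57%).

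**CACE on the same data.** Let e be the effect of assignment on non-attenders. The as-randomised difference is a·d + (1 − a)·e. Dividing by a gives d + e(1 − a)/a, which equals d when e = 0. Its SE at a = 0.7 is about 5.3·√(2/101) / 0.7 = 1.07 mg, against 0.82 mg for PP.

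**Simulation** (101 per arm, 4,000 replicates, a = 0.7; mean estimates in mg):

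| g | d | e | As randomised | PP | CACE |
|---|---|---|---|---|---|
| +2 | 0 | 0 | 0.00 | +0.60 | −0.01 |
| +2 | 2.1 | 0 | 1.46 | 2.70 | 2.07 |
| −2 | 2.1 | 0 | 1.45 | 1.47 | 2.08 |
| +2 | 2.1 | 0.5 | 1.60 | 2.69 | 2.29 |

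In the first row, PP rejects in 11.6% of replicates and the as-randomised test in 4.7%. The last row breaks the exclusion restriction, and the CACE then overshoots 2.1.

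**The case against.** A reader might infer three stronger things from the PP rule. The document supports none of them.

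**That the rule favours the intervention.** This is plausible, because attenders may be more motivated. But the SAP gives no attendance rate and no attender/non-attender gap, and the bias is zero at g = 0 and negative for g below zero. Only the gap left after adjustment for baseline activity, gender and ethnicity counts, and a residual gap of 2 mg is nearly as large as the whole target difference. Section 1.2.4 also requires willingness and ability to attend, which may raise attendance and narrow the gap. At 90% attendance and 1 mg the bias is only 0.10 mg.

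**That a CACE is free of bias and should replace the PP analysis.** A CACE removes the selection term but needs the exclusion restriction. Section 1.2.3 leaves it open whether non-attenders receive the texts. A CACE is also less precise and, on complete cases, keeps any bias from missing outcomes.

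**That the trial's main result is compromised.** It is not. The complete-case primary analysis keeps non-attenders who have outcome data (sections 3.2 and 5.2.1), and the imputed ITT analysis includes everyone randomised (section 3.3). The robustness aim stated in sections 2.1 and 3.1 concerns missing data; the SAP does not claim it for the PP set.

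These limits stand. They leave untouched the one-arm exclusion, and with it the fact that the PP contrast is not randomised.

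**Conclusion.** The point holds as a cheap improvement to a sensitivity analysis. The PP comparison is non-randomised and is biased for the effect in attenders by (1 − a)·g. That is +0.1 to +1.2 mg (5% to 57% of 2.1 mg) under assumed attendance of 60% to 90% and an assumed residual gap of 1 to 3 mg, and zero or negative if the gap is. The formula is exact given its definitions; the size and sign rest entirely on assumptions.

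A CACE suits this design as an addition. Controls do not receive the programme, so non-compliance is one-sided. If assignment affects nobody, the exclusion restriction holds automatically, so the CACE carries no selection bias in the case where the PP estimate can.

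Section 5.2.2.1 also needs tidying. Read literally, its attendance criterion would remove every control. Section 3.4 makes the intended set clear, so this is a wording mismatch and not a second definition.

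**What to change.** 1. **Add a CACE beside the PP analysis.** Use two-stage least squares with randomised arm as the instrument for attending at least one session, the same baseline covariates as the primary model (gender, ethnicity, baseline activity), and all participants with outcome data in both arms.
2. **State its assumptions.** Say that assignment is assumed to have no effect on those who attend no session, and record whether they receive the text messages. The leaflet goes to both arms, so it does not threaten this assumption. Say that the interval will be wider than for PP and that complete-case limits still apply.
3. **Label the PP estimate as non-randomised**, and do not cite it as evidence that the primary finding is robust.
4. **Align section 5.2.2.1 with section 3.4** by limiting the attendance criterion to the intervention arm.

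The cost is one standard Stata command and a few lines of SAP text. Attendance is already needed to define the PP set, so no new data are required, and the sample size does not change.

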# 4 General Issues for Statistical Analysis

# 4.1 Multiplicity, Multiple Comparisons and Interim Analyses

All tests and reported p-values will be two-sided, where a p-value of < 0.05 will be considered to be statistically significant. Estimates will be presented with 95% confidence intervals. There will be no formal adjustment for multiple significance testing. The outcomes however, are clearly categorised by the degree of importance (primary and secondary). No formal interim analyses were planned.

## 4.2 Analysis Software

All data manipulations, tables, figures and analyses will be performed using Stata version 15.0 . The validated program code (do file) and any other outputs created shall be documented and archived together.

# 5 Statistical Methodology

## 5.1 Demographic and Baseline Characteristics

Demographic and baseline characteristics for individual participants will be summarised by randomisation group. Numbers (with percentages) for binary and categorical variables and means (and standard deviations), or medians (with lower and upper quartiles) for

v 1.0

Date:

20/03/2019

Clinical Trials Unit

continuous variables will be presented. The number of missing values will be reported in the footnote of the summary table. There will be no tests of statistical significance nor confidence intervals for differences between randomised groups on any of the baseline variables.

### 5.2 Primary Endpoint Analysis

### 5.2.1 Primary Analysis of Primary Endpoints

The primary outcome is change in overall volume of physical activity (average acceleration, ENMO) from baseline to 12 months. For the primary outcome treatment arm will be compared using linear regression modelling with

- 1. a binary indicator for randomisation group as the explanatory variable
- terms for stratification factors (gender and ethnicity) as confounders
- 3. adjustment for the change from baseline in accelerometer wear time and baseline average daily physical activity.

The primary analysis at 12 months will be based on complete data.

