#### Clinical Trials Unit

#### 1.2.2 Randomisation

Participants will be randomised 1:1; stratified by gender (male; female) and ethnicity (White European; other) to either intervention or control groups.

If two people are taking part from the same household they will be randomised to the same arm to prevent contamination taking place.

Control participants will be sent a standard information booklet and letter informing them of their results and the outcome of randomisation. Intervention participants will also be sent a letter informing them of their results and the outcome of randomisation and subsequently contacted to book them onto an education programme.

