### Clinical Trials Unit

#### 1.2.4 Inclusion Criteria

- Aged 18 years or older
- 12-36 months post confirmed diagnosis of a cardiac event (myocardial infarction, angina or acute coronary syndrome)
- Able to speak and read English to participate effectively in a group education programme
- Willing and able to attend the education sessions and clinic visits
- Willing and able to give informed consent.
- Access to a mobile phone in order to receive text messages
- Willingness to allow GP notification of their participation in study and access to patient records for purpose of study
- Able to take part in moderate physical activity as assessed using Incremental Shuttle Walk Test (ISWT) (Level three or above)

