#### 1.2.6 Sample size calculations

The primary outcome is change from baseline to 12 months average daily physical activity, as quantified by the Euclidean norm minus one (ENMO) method measured in milligravity units (mg). This is the main measure of activity derived from the activity monitor that will be used in this study (PACES). In order to detect a minimum clinically significant difference of 2.1 mg, which is equivalent to an overall increase in physical activity volume of approximately 30 minutes of light walking at 4km/h, assuming a standard deviation of 5.3 mg [1], a power of 80% and significance level of 5%, the sample size requires 202 participants. To allow for 20% loss to follow-up and 10% noncompliance of the activity monitor, we will therefore need to recruit 290 participants (145 in each group).

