## 5.4 Subgroup Analyses

We will conduct the following subgroup analyses to assess if the intervention effect is statistically different between these groups.

- Ethnicity
- Gender
- Age < 60 & ≥ 60 years

- ISWT: High risk < 420 & Low risk ≥ 420

- Cardiac condition (MI, Angina or ACS)

The main analysis for each subgroup will involve using the same analytic principles as the primary analysis, but stratifying by the subgroup to estimate the mean difference in average daily physical activity when compared to the control group. Further subgroup analyses will investigate the interaction effects between the treatment and subgroup, this will include an

v 1.0

Date:

20/03/2019

additional interaction term to the model; 'subgroup x treatment'. Subgroup results will be graphically presented as forest plots, with the estimated difference of average daily physical activity between treatment groups with 95% confidence interval for the interaction.

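### Adding baseline ISWT distance and age to the primary model would be a cheap, optional improvement to a model that is already valid

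*SAP*

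**What the plan says.** SAP 5.2.1 specifies a linear regression of 12-month change in average acceleration with "a binary indicator for randomisation group as the explanatory variable", "terms for stratification factors (gender and ethnicity) as confounders" and "adjustment for the change from baseline in accelerometer wear time and baseline average daily physical activity". SAP 1.2.2 names the same two stratification factors: "Participants will be randomised 1:1; stratified by gender (male; female) and ethnicity (White European; other". Every stratification factor is therefore in the model, as is the baseline value of the outcome.

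The ISWT appears in three other places:
- SAP 1.2.4 makes it an entry test: "Able to take part in moderate physical activity as assessed using Incremental Shuttle Walk Test (ISWT) (Level three or above".
- SAP 2.2 lists the distance in metres among the measures taken at baseline and 12 months.
- SAP 5.4 uses it as a subgroup factor: "ISWT: High risk < 420 & Low risk ≥ 420".

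Age is also a subgroup factor in 5.4: "Age < 60 & ≥ 60 years".

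The primary analysis is complete-case (SAP 2.1, 3.2 and 5.2.1). The sample size in 1.2.6 is inflated for missing outcomes: "To allow for 20% loss to follow-up and 10% noncompliance of the activity monitor". Multiple imputation is a sensitivity analysis. SAP 5.2.2.2 imputes 12-month and baseline activity from randomised group, sex and ethnicity.

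**The concern.** With up to 30% of outcomes missing, the covariate list of a complete-case regression is also part of how missing data are handled. Such a model guards against outcome-related drop-out only through the variables it conditions on. Fitness and age could plausibly relate to both 12-month activity and staying in the trial. The arms also make different demands: two group sessions and 82 activity texts against a leaflet (SAP 1.2.3). Both values are known before randomisation, so conditioning on them is safe.

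Two things could be gained: a slightly narrower interval for the primary comparison, and protection against one particular form of drop-out bias. The imputation analysis does not supply that protection, because neither variable is among its predictors. Reusing the primary covariates when the imputed data are analysed does not put them into the imputation step.

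**Working it through.** **Planned sample size.** Inputs from SAP 1.2.6 and 4.1: difference 2.1 mg, SD 5.3 mg, 80% power, two-sided 5%.
- Normal approximation: n per arm = 2 × (1.96 + 0.842)² × 5.3² / 2.1² ≈ 100. The t-test version gives 100.96, so 101 per arm and 202 in total, as stated.
- 202 / 0.70 = 288.6, so 289, or 290 for equal arms, as stated. Expected completers: 290 × 0.70 = 203.
- The full SD of 5.3 mg is used, with no credit for covariates. Planned power therefore does not depend on which covariates are added.

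**Precision.** Let R² be the share of residual variance that ISWT and age explain beyond the existing terms. The SAP gives no value, so a range is assumed. With 101 per arm, SE = 5.3 × √(1 − R²) × √(2/101).

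The planned model has six coefficients including the intercept, so about 203 − 6 = 197 residual degrees of freedom. Two more terms leave 195 and cost about √(197/195) = 1.005 in SE. Simulation put this cost at 0.5-0.8%. The net columns use 1.005.

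| Assumed R² | SE before cost (mg) | Net SE against plan | Net power |
|---|---|---|---|
| 0 | 0.746 | +0.5% | 80.0% |
| 0.01 | 0.742 | 0.995 × 1.005 = 1.000, no change | 80.4% |
| 0.05 | 0.727 | 0.975 × 1.005 = 0.980, −2.0% | 82.0% |
| 0.10 | 0.708 | 0.949 × 1.005 = 0.953, −4.7% | 84.0% |

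Net power is Φ(2.1 / net SE − 1.96); for R² = 0.05, Φ(2.1 / 0.7306 − 1.96) = 82.0%. The planned model has 80.4% on the same formula. With a cost of 0.8%, the last two SE reductions become 1.8% and 4.4%. So the gain is nil near 1% and about 2% to a little over 4% at 5-10%.

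**Drop-out, harmful case.** Simulation inputs: 290 randomised, about 30% missing, true effect 2.1 mg, 4,000 trials per setting. Assumed: correlation of ISWT with baseline activity 0.4; higher ISWT goes with a larger change; low ISWT raises drop-out in the intervention arm only. Mean estimates, planned model / with ISWT:

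| ISWT effect on change (mg per SD) | Log-odds of drop-out 0.7 per SD | Log-odds 1.0 per SD |
|---|---|---|
| 0.5 | 2.18 / 2.10 | 2.22 / 2.11 |
| 1.0 | 2.26 / 2.09 | 2.33 / 2.10 |
| 1.5 | 2.34 / 2.09 | 2.44 / 2.10 |

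The planned model is too high by 0.08 to 0.34 mg, and its 95% interval covers as little as 91.6% at worst. With ISWT added, the estimate returns to 2.09-2.11. Against the planned SE, 0.1-0.3 mg is 0.1/0.746 = 0.13 to 0.3/0.746 = 0.40 of an SE. The 1.5 mg row implies an extra R² of 1.5² × (1 − 0.4²) / 5.3² = 6.7%.

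**Drop-out, symmetric case.** With ISWT driving drop-out equally in both arms, the mean estimate was 2.10 with or without ISWT. A separate large-sample run, with about 28% missing and extra R² of 2%, 5% and 10%, gave deviations of at most 0.06 mg. These were practically the same in both models, so they are simulation noise.

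**Age.** The simulations of the harmful case used ISWT values. No figure shows drop-out bias through age.

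**The case against.** A reader might infer that the primary model is misspecified, biased or short of power because an entry test and two subgroup factors are missing from it. The SAP does not support that.

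- The model holds both stratification factors and the baseline outcome, usually the strongest prognostic covariate. Leaving further covariates out of a linear model does not in itself bias a randomised comparison.
- An entry test or subgroup factor need not be a main effect. Cardiac condition is also a subgroup factor in 5.4 and also outside the model.
- Planned power is met without the change, and the precision gain rests on an R² that the SAP does not give.
- The bias needs two conditions that the SAP does not state: drop-out that depends on ISWT differently by arm, and ISWT predicting change beyond baseline activity.

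All of this stands, and it limits the point to an optional improvement. One part of the case for change survives. The statement about omitted covariates is assured with full follow-up, but not automatically among completers, and the planned imputation would not reveal the problem because it uses neither variable.

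**Conclusion.** Minor. The primary analysis is valid as written, and nothing in the SAP is contradicted. Adding ISWT distance and age is worthwhile because it costs almost nothing, not because the plan fails without it.

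The SE gain runs from nil to about 2-4% as the assumed extra R² goes from about 1% to roughly 5-10%. The protection against bias, roughly 0.1-0.3 mg or 5-14% of the 2.1 mg target, applies only if low ISWT drives drop-out mainly in the intervention arm and ISWT predicts change beyond baseline activity. The upward direction also depends on fitter participants showing the larger change. Under symmetric drop-out the protection is worth nothing. Age is proposed for precision only.

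**What to change.** Amend the SAP before database lock, so that the choice is prespecified.

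1. In 5.2.1, add to the covariates: *baseline ISWT distance (metres, continuous) and age (years, continuous)*. The per-protocol analysis (5.2.2.1) and the subgroup models (5.4) reuse the primary model and would inherit both terms.
2. In 5.2.2.2, name ISWT distance, age and baseline activity as predictors of the 12-month value in the imputation model itself. Carrying the primary covariates into the estimation step alone is not enough.

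Cost: a few lines of SAP text and two degrees of freedom of about 197, which raises the SE by about 0.5-0.8% if neither variable is prognostic. Under the by-analysis rule in 3.2, anyone without a recorded ISWT distance would drop out of the complete-case analysis. That should be rare because the ISWT is an entry test, but the SAP does not say that the distance is complete, so the number affected should be reported.
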